### General Study Design

This section describes the role of the clinical team in participant recruitment and the consent process. Also described is participant procedures and involvement in the study. Further information on initial procedures and the recruitment process can be found in **Section 5.5 Strategies for Recruitment and Retention**.

Patient enters Sickle Cell Clinic for routine appointment. During their visit while waiting to be seen, the Research Assistant directs them to the Kiosk where they can learn about CaRISMA.

At the Kiosk, the patient watches the consent video and completes guided prompts to learn about the study. This is followed by a set of study comprehension questions. After informed consent, the patient is asked to complete a set of questionnaires for the baseline measures.

[figure not shown]
Immediately once a patient submits a signed consent form on the Kiosk or electronic web system, the Research Assistant is alerted on their study cell-phone.

In the same clinic visit, the Research Assistant approaches the now-consented patient. Using her own cell-phone or a study provided mobile device, he guides her through downloading the app, interacting with the chatbot, and links her to the CaRISMA Facebook page. In the first use of the chatbot, the patient is randomized based on their study ID into one of two study arms (CBT or Education).

The patient leaves the clinic and interacts with the virtual intervention at her own pace.

Within 24 hours of consenting, one of the health coaches contacts the patient. The health coach informs the patient that they will have weekly one-on-one check-ins throughout the duration of the intervention.

Through text message or email, the patient receives a link to our online survey tool to complete the follow-up questionnaires at 3, 6, and 12-month time points. The patient continues completing modules with the intervention, which includes interactive video lessons.

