Sample Size Calculation. For the primary test of comparative effectiveness of digital CBT versus mobile education (m-Education) for the trial, the power calculation is based on the comparison of intervention groups for the main outcome of the 6-month change in pain interference. Specifically, our sample size of 350 participants enables 80% power to detect a difference of 0.37 SDs between study arms on 6-month changes. This detectable effect is also applicable to key secondary outcomes, such as pain intensity and depression, as measured by the PHQ-9. Our calculations account for 15% attrition at 6 months.

Hypotheses. Our study hypotheses are:

H1: cCBT will confer greater benefit on pain outcomes at 6 months, compared to m-Education. The primary outcome of the proposed trial is change in pain interference at 6 months. The main secondary outcome will be change in average weekly pain intensity. We will also explore sustainability of the intervention effects at 12 months.

H2: cCBT will confer greater benefit on depressive symptoms at 6 months, compared to m-Education.

H3: cCBT will confer greater decreases in health care utilization (opioid prescriptions, acute care visits) and opioid misuse behaviors (Current Opioid Misuse Measure – COMM) over 12 months, compared to m-Education.

Analysis Sets. All analyses will be under the framework of intention-to-treat, such that all randomized participants are included regardless of initiation or adherence to interventions. However, we will conduct sensitivity analyses restricting to participants who were randomized with confirmation of sickle cell disease.

Study Outcomes.

Primary Pain Outcome: Pain Interference

Patient Reported Outcomes Measurement Information System Pain Interference assesses the effect of patient-reported pain on relevant aspects of a person's life and may include the extent to which pain hinders engagement with social, cognitive, emotional, physical, and recreational activities. This measure will only be completed at baseline and 3, 6, and 12 months.

Secondary Pain Outcome: Daily Pain Intensity

Participants will be asked to enter their daily pain via a mobile website. They will receive reminder notifications via text messages for 2-week periods at baseline and 3, 6, and 12 months. However, between these automated-reminder periods, participants will be encouraged to continue entering their pain scores on the mobile pain web app.

Other Secondary Outcomes

Painimation

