Linear mixed models will be employed for the primary outcome of pain interference as a function of time, study arm (digital CBT vs Education), time \times study arm interaction, study site, and baseline depression level (PHQ-9 \leq 10 vs PHQ-9 $>$ 10). We will account for multiple observations for each participant by including a random effect for the subject. In addition, baseline variables with large, clinically meaningful between-arm differences will be included as covariates in the secondary analyses. Contrasts will be estimated to assess the impact of digital CBT and education intervention on 6-month improvements in pain interference. As a secondary investigation, we will use the same linear mixed models to address whether the 6-month improvements are sustainable for 12 months. The analytic strategy for the key secondary outcome of pain intensity will be identical to that of the primary outcome. As the confirmation of a sickle cell diagnosis may not be made immediately after randomization, we will conduct an a priori sensitivity analysis restricting eligible participants with the confirmation of SCD.

Analysis of Secondary Outcomes

Secondary outcomes such as PHQ-9, Current Opioid Misuse Measure, GAD-7, Adult Sickle Cell Quality of Life Measurement Information System, and SCSES will be analyzed using similar linear mixed models with time, study arm, time×study arm interaction, study site, and baseline depression level as fixed covariates and a random effect for each subject. Health care use will be compared between study arms using generalized linear models to account for count data (i.e., Poisson regression) for each of the following: the number of opioid prescriptions, number of emergency department visits, and number of hospitalizations over 12 months after study entry. Predictors will include the study arm, study site, and baseline depression level. The corresponding health care use in the 12 months before study entry will be entered as a covariate in each model. We will offset each model by the participant's time in the study.

Subgroup Analysis

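### Pain interference, primary model: a common baseline mean for both arms would cut the variance of the 6-month contrast by about 13–27% (assumed correlation 0.7–0.4), provided baseline precedes randomisation

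*SAP*

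**What the plan says.** The SAP, under Analysis of Primary and Secondary Pain Outcomes, sets out the primary model: "Linear mixed models will be employed for the primary outcome of pain interference as a function of time, study arm (digital CBT vs Education", followed by the interaction of the two, recruiting site, baseline depression in two levels and a random effect for each participant. The quantity tested is the arm contrast in 6-month improvement. Protocol 9.4.2 lists the same terms, also without a baseline pain term. It names pain intensity as primary; the SAP names pain interference, and I follow the SAP.

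Other baseline variables have one way in: "baseline variables with large, clinically meaningful between-arm differences will be included as covariates in the secondary analyses".

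The coding of time is not stated. The SAP does treat 12 months as a separate question: "we will use the same linear mixed models to address whether the 6-month improvements are sustainable for 12 months". That fits visits as categories but does not say so.

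Pain intensity inherits whatever is done for the primary outcome: "The analytic strategy for the key secondary outcome of pain intensity will be identical to that of the primary outcome".

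On attrition: "Our calculations account for 15% attrition at 6 months". Pain interference is collected at baseline and at 3, 6 and 12 months, so the score needed for the improvement is already in the data.

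**The concern.** Before treatment, randomised arms have the same expected pain interference. A model with a free arm effect at baseline nevertheless estimates two baseline means, and subtracting them carries the chance baseline difference into the 6-month contrast. Holding the baseline mean common to both arms removes that component.

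No other term does this work. The depression term is constant over time, so it has almost no effect on the precision of a within-participant change. The imbalance rule operates only in secondary analyses and only after a large difference has been seen.

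What is at stake is precision alone: a wider interval for the primary comparison than the trial's own data require.

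**Working it through.** **The plan's own figure.** The SAP's Sample Size Calculation gives 350 participants, 80% power, 0.37 SD of 6-month change and 15% attrition. No alpha is stated for the primary test. At an assumed two-sided 0.05:

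- n per arm = 2(1.960 + 0.842)²/0.37² = 114.7, so 115 per arm or 230 in total, and 230/0.85 = 271 after attrition.
- With 350 randomised, 350 × 0.85 = 297.5 are observed, and power for 0.37 SD is 89.1%.

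The stated combination therefore does not reproduce at that alpha. This is a separate matter: the variance ratio below depends only on the correlation and the attrition.

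**Inputs.**
- Allocation 1:1, n = 175 per arm (Protocol synopsis and 4.1).
- Fraction missing at month 6, a = 0.15 (SAP). Those missing are treated as having baseline only, in line with the 10–15% with no follow-up expected in Protocol Table 5.
- rho, the correlation of baseline with month 6 given site and depression level: **not in the documents; 0.4–0.7 assumed, 0.3–0.8 also shown.**
- s, a common SD at each visit; it cancels.

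**Formulas**, visits as categories:
- Planned, free baseline means: V1 = (2s²/n) × [(1 − rho)² + (1 − rho²)/(1 − a)]
- Common baseline mean: V2 = (2s²/n) × (1 − rho²)/(1 − a)
- Ratio: V2/V1 = 1/[1 + (1 − a)(1 − rho)/(1 + rho)]

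The term (1 − rho)² is the cost of estimating the two baseline means separately.

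Example, rho = 0.7: planned bracket 0.09 + 0.51/0.85 = 0.690; common baseline 0.600; ratio 0.600/0.690 = 0.870. With s = 1 the standard errors are √(2 × 0.690/175) = 0.0888 and √(2 × 0.600/175) = 0.0828.

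| rho | planned bracket | common baseline | ratio | variance cut | interval narrower, 1 − √ratio | N matching 350 as planned, 350 × ratio rounded up |
|---|---|---|---|---|---|---|
| 0.3 | 1.561 | 1.071 | 0.686 | 31.4% | 17.2% | 241 |
| 0.4 | 1.348 | 0.988 | 0.733 | 26.7% | 14.4% | 257 |
| 0.5 | 1.132 | 0.882 | 0.779 | 22.1% | 11.7% | 273 |
| 0.6 | 0.913 | 0.753 | 0.825 | 17.5% | 9.2% | 289 |
| 0.7 | 0.690 | 0.600 | 0.870 | 13.0% | 6.7% | 305 |
| 0.8 | 0.464 | 0.424 | 0.914 | 8.6% | 4.4% | 320 |

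**Checks** (variance cut at rho 0.7 and at rho 0.4):
- Four visits, random intercept, 15% with baseline only: 13.0% and 26.7%.
- Four visits, monotone dropout of 7.5/15/22.5%: 13.2% and 26.8%.
- Four visits, only month 6 missing: 13.5% and 27.1%.
- Seven site strata and depression added, dropout 10/15/20%: 12.7% and 26.2%.
- Simulation: 12.4% and 26.9%.
- No attrition, where the cut is (1 − rho)/2: 15% and 30%.
- Time coded as linear, 15% with baseline only: 10.5% and 25.2%.

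**Order of baseline and randomisation**, from the documents:
- Protocol 4.1, General Study Design: "After informed consent, the patient is asked to complete a set of questionnaires for the baseline measures". Randomisation comes later, at first use of the chatbot.
- Protocol 8.1 has the questionnaires completed as soon as the person is accepted. Sections 5.1 and 5.4 have people who are never randomised complete baseline questionnaires too. Both suggest that the questionnaires come first.
- A later paragraph of 4.1 describes randomisation at first opening of the program and only then the link to the baseline questionnaires.
- The SAP's Randomization paragraph ties allocation to eligibility and does not mention the baseline questionnaires.

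**The case against.** **Nothing is wrong with the planned contrast.** This stands. The SAP defines the outcome as change at 6 months, bases its power on change and estimates change. A reader might infer bias or a threat to the 80% power; the documents support neither. At the assumed two-sided 0.05, 350 participants give more than 80% for 0.37 SD. Nor does the Protocol 9.2 remark on recruitment in sickle cell trials show a need: it explains why 1400 participants are not sought for Aim 2.

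**The size is uncertain.** This also stands. Neither rho nor the coding of time is given. The gain is positive for every rho below 1, but it shrinks as rho rises.

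**Health care use.** For those models the SAP says "The corresponding health care use in the 12 months before study entry will be entered as a covariate in each model". A reader might infer that the plan is inconsistent. It is not: those models have one post-entry count per person, so the prior value can enter only as a covariate, whereas the mixed model already has baseline among its responses.

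**Pain intensity.** A reader might extend the gain there because the strategy is shared. The documents do not support that. Protocol 6.1.1 and 6.1.2 place the diary inside the intervention, and 4.1 has first opening of the intervention trigger randomisation, so the baseline diary window may follow allocation. The SAP speaks of a mobile website, so this is not certain. A reader might also infer from the 2-week reminder periods ("They will receive reminder notifications via text messages for 2-week periods at baseline and 3, 6, and 12 months") that the diary outcome is undefined; the SAP's H1 defines it as average weekly pain intensity.

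**Baseline as a covariate.** A reader might take this as interchangeable with a common baseline mean. In precision it nearly is: in month-6 completers the standard errors are 0.1063 against 0.1060 at rho 0.4, and 0.0828 against 0.0824 at rho 0.7. But it drops participants with no follow-up, and the SAP's analysis set is all randomised participants.

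**Conclusion.** The point holds as an optional gain in precision for the primary outcome, pain interference, and not as an error. The planned contrast is valid and unbiased, but it leaves unused information that the trial already collects. With categorical visits and 15% attrition, a common baseline mean cuts the variance of the 6-month contrast by about 13% (rho 0.7) to 27% (rho 0.4), or about 9% to 31% over rho 0.8 to 0.3. With linear time the cut is about 10.5% to 25% for rho 0.7 to 0.4.

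The conclusion rests on an assumed correlation, on equal SDs across visits, on missing data that a likelihood analysis can handle, and on baseline questionnaires that precede randomisation. The protocol suggests that order but does not settle it. The existing model has a stake in the answer too, because its PHQ-9 term comes from the same questionnaire set.

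**What to change.** 1. Confirm from the data-capture time stamps, or by reconciling the paragraphs of Protocol 4.1, that the baseline questionnaires precede randomisation. If they do not, keep the planned contrast and stop here.
2. If they do, state in the SAP that time is categorical (0, 3, 6 and 12 months) and that both arms share one baseline mean, with arm effects only at months 3, 6 and 12. Keep site, depression level and the random subject effect. Prefer this to the covariate form, because it retains every randomised participant who has a baseline score.
3. Carry the same form into the subgroup and mediation models, which are built on the primary model. In the subgroup model the baseline mean may differ by depression level but not by arm.
4. Limit the sentence that gives pain intensity an identical strategy, so that the constraint does not pass to the diary outcome unless a diary baseline from before randomisation is confirmed.

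The cost is SAP wording and one check of timing: no new data, no change of outcome and no change of analysis set. The change should be settled before outcomes are examined by arm, since a later switch would look data-driven.

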### 9.4.2 ANALYSIS OF THE PRIMARY ENDPOINT(S)

We will employ linear mixed models for the primary outcome of pain intensity and the secondary outcome of pain interference (Hypothesis 1) as a function of time, study arm (cCBT vs. m-Education), time-by-study arm interaction, study site, and baseline depression level (PHQ-9  $\leq$  10 vs. PHQ-9  $>$  10). We will account for multiple observations for each participant by including a random effect for subject. Additionally, baseline variables with large clinically meaningful between-arm differences will be included as covariates. Contrasts will be estimated to assess the impact of cCBT and m-Education intervention on 6month improvements in pain. As a secondary investigation, we will use the same linear mixed models to address whether the 6-month improvements are sustainable to 12 months.

We will answer Hypothesis 2 using a similar analytic strategy. Depression (PHQ-9) will be modeled as a function of time, study arm, time-by-study arm interaction, and study site. We will account for multiple observations for participant by including a random effect for each subject.

Healthcare utilization (Hypothesis 3) will be compared between study arms using generalized linear models to account for count data (i.e., Poisson regression) for each of the following: the number of opioid prescriptions, number of ED visits, and number of hospitalizations over 12 months post study entry. Predictors will include study arm, study site, and baseline depression level. The corresponding health care utilization in 12 months prior to study entry will be entered as a covariate in each model. We will offset each model by participant's time on the study.

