Cognitive Behavioral Therapy and Real-Time Pain Management Intervention for Sickle Cell Via Mobile Applications (CaRISMA)

NCT04419168

1/13/2023

Statistical Analysis Plan

Study Design & Objectives. CaRISMA is a multisite, randomized, pragmatic, comparative effectiveness trial that will be conducted at 6 comprehensive sickle cell centers and 4 community-based organizations (CBOs). A total of 350 adults with SCD who report chronic pain and/or use long acting or daily opioids will be enrolled and randomized in a 1:1 ratio to receive either a digital CBT program tailored for adults with SCD (CBT) or pain and SCD education (Education) on their mobile phones for 12 weeks. Both programs will use identical mobile-based technology platforms, with the only difference being the content provided. The focus of the digital CBT program is to teach behavioral coping skills through participants' seeing and doing, whereas the pain education arm focuses on improving self-management through participants' learning and knowing more about pain and SCD.

The primary objective of the CaRISMA (Cognitive Behavioral Therapy and Real-time Pain Management Intervention for Sickle Cell via Mobile Applications) trial is to compare the effectiveness of two mobile phone-delivered programs for reducing SCD pain symptoms at the 6-month follow-up: digital CBT versus pain and SCD education (Education). We will also evaluate the sustainability of the intervention effects at the 12-month follow-up. The secondary objective is to assess whether baseline depression symptoms moderate the effect of interventions on pain outcomes. We hypothesize that digital CBT will confer greater improvement in pain interference, pain intensity, and depressive symptoms at 6 months compared with Education. We also hypothesize that digital CBT will confer a greater reduction in health care use (e.g., opioid prescriptions or refills or acute care visits) over 12 months compared with Education.

Randomization. Upon completion of eligibility, participants will be randomly assigned to either digital CBT or Education. Permuted block randomization will be stratified by study center (e.g., one of the six clinical sites or from a community partner) in an effort to control for site-specific disease education and treatment approaches. The randomization schema was created by the lead statistician in the data coordinating center and integrated into the web-based data capture system.

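### Baseline variables entered as main effects cancel from the 6-month change contrast, so the planned chance-imbalance analysis cannot correct for an imbalanced predictor of change

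*SAP*

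**What the plan says.** The SAP section Analysis of Primary and Secondary Pain Outcomes models pain interference on time, arm and their interaction, followed by "study site, and baseline depression level". Within-person correlation is handled as follows: "We will account for multiple observations for each participant by including a random effect for the subject". The effect is then read off: "Contrasts will be estimated to assess the impact of digital CBT and education intervention on 6-month improvements in pain interference". For chance imbalance the rule is that "baseline variables with large, clinically meaningful between-arm differences will be included as covariates in the secondary analyses".

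Protocol 9.4.2 has the same structure ("time-by-study arm interaction, study site, and baseline depression level"). Its imbalance rule is similar but is not confined to secondary analyses: "baseline variables with large clinically meaningful between-arm differences will be included as covariates". The SAP repeats the model for the secondary scales, with "study site, and baseline depression level as fixed covariates and a random effect for each subject".

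Pain interference is collected at 0, 3, 6 and 12 months, and no baseline pain score is listed as a predictor. The natural reading is that the baseline value is part of the response. Time interactions with a baseline variable appear only in the separate depression subgroup model. The SAP does not say outright that baseline is in the response, that the subject effect is only an intercept, or that imbalance covariates enter without a visit interaction.

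**The concern.** The imbalance analysis exists to show whether a chance difference between the arms could explain the result. If the added variables cannot move the reported contrast, adjusted and unadjusted estimates will agree almost whatever the imbalance. A reader of the trial report would take that agreement as evidence of robustness when it follows from how the model is written. What is at stake is the meaning of this secondary analysis, for pain interference and for the other outcomes analysed with the same model.

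**Working it through.** **1. The plan's own figure.** The 0.37 SD difference in 6-month change (SAP, Sample Size Calculation) serves here only as a yardstick. With 350 participants and 15% attrition, each arm has 350 × 0.85 / 2 = 148.75. In SD units the standard error is √(2/148.75) = 0.116, and 0.37/0.116 = 3.19. At two-sided 0.05 (assumed; Protocol 9.4.6 states it for the interaction tests), 3.19 − 1.96 = 1.23, which gives about 89% power, not the stated 80%. Nothing below depends on that gap.

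**2. Algebra.** Write the model for person i at visit t, with arm A and baseline variable x, as

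y(i,t) = μ(t) + αA(i) + δ(t)A(i) + γx(i) + b(i) + e(i,t), with δ(0) = 0.

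The change to 6 months is

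y(i,6) − y(i,0) = [μ(6) − μ(0)] + δ(6)A(i) + e(i,6) − e(i,0).

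The terms γx(i) and b(i) have gone. With complete data, the estimate of δ(6) and its standard error are therefore the same whether or not x is in the model. If x predicts change, so that γ varies with visit, the bias is

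[γ(6) − γ(0)] × (between-arm difference in mean x),

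and only an x-by-visit term can remove it. If x affects only the level of pain, γ(6) = γ(0) and the bias is zero.

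**3. Simulation.** Inputs from the documents: N = 350, 1:1 allocation, visits at 0, 3, 6 and 12 months, 15% attrition. Assumed: intraclass correlation 0.5, seven site strata, 40% high depression, no true arm effect, a 0.3 SD imbalance in x, and an effect of x on 6-month change of 0.2 SD per SD. Expected bias is 0.3 × 0.2 = 0.06 SD, and 0.06/0.37 = 16% of the design difference. Site, depression and x were entered together. The table gives the mean 6-month contrast (mean standard error) over 300 trials.

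| Dropout at 6 months | No covariates | Main effects | All covariates × visit |
|---|---|---|---|
| None | 0.0686 (0.1080) | 0.0686 (0.1080) | 0.0084 (0.1093) |
| 15%, independent of x | 0.0569 (0.1149) | 0.0569 (0.1146) | −0.0040 (0.1162) |
| 15%, depends on x | 0.0572 (0.1168) | 0.0618 (0.1164) | 0.0035 (0.1179) |
| 40%, independent of x | 0.0543 (0.1319) | 0.0557 (0.1311) | −0.0001 (0.1335) |
| 40%, depends on x | 0.0483 (0.1352) | 0.0511 (0.1343) | −0.0032 (0.1369) |

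The Monte Carlo error of a mean in the first row is about 0.108/√300 = 0.006. With complete data, main effects changed the contrast in a single trial by at most 3e-15. With 15% dropout they moved it by 0.008 to 0.010 on average (maximum 0.038), without removing any of the bias.

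**4. Covariance structure.** Random-slope and unstructured covariances gave the same result. With complete data the main effect changed the contrast by at most 4e-14, while factor × visit removed about 0.06 (random slope: 0.0597 to 0.0011).

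**5. Where main effects do work.** Suppose depression affects only the level of pain (by 0.8 SD) and dropout is concentrated in high-depression participants of one arm. With 35% dropout in that cell, the mean contrast under no effect was −0.022 without the covariate and 0.010 with the main effect. With 50% it was −0.049 and 0.007 (Monte Carlo error 0.010).

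**6. The alternative model.** In one simulated complete data set, the model with baseline in the response gave 0.0247 (SE 0.1047) with and without main effects, and −0.0905 with visit interactions. Modelling only post-baseline scores with baseline as a covariate gave 0.0678 without the other covariates and −0.108 with them as main effects. In that model, main effects do adjust.

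**The case against.** A reader might infer that these covariates are wholly inert. The documents do not support that: the SAP allows for 15% attrition and uses a likelihood-based analysis, and step 5 shows main effects correcting dropout that depends on covariate and arm. That stands.

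A reader might also infer that the primary model must be rebuilt with site-by-visit terms. It need not be. The SAP stratifies randomisation by centre "in an effort to control for site-specific disease education and treatment approaches", so site is balanced by design. Site × visit and depression × visit together would cut the standard error by about 2%, if site has an assumed SD of 0.25 and depression an assumed effect of 0.3 SD on change. Against that, site × visit costs (7 − 1) × 3 = 18 parameters with seven strata. If each of the SAP's six centres and four community organisations is a stratum, it costs (10 − 1) × 3 = 27. Protocol Table 5 expects only 50 community-recruited participants, so some cells could be sparse.

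The model form is inferred. The SAP puts baseline depression level into the PHQ-9 model, which is odd if baseline PHQ-9 is itself in the response (Protocol 9.4.2 leaves it out of that model). This is a fair reason to ask for the model to be stated, but no baseline pain score is listed as a predictor, so the reading used here remains the natural one.

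Finally, the example is uncommon. A 0.3 SD imbalance at 175 per arm is 0.3/√(2/175) = 2.8 standard errors (p about 0.005), and a bias of 0.06 is about half of one standard error of the contrast. True, but the SAP reserves this analysis for large imbalances, so that is the case it has to handle.

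**Conclusion.** On the natural reading of the SAP, the chance-imbalance analysis cannot remove bias from an imbalanced variable that predicts change in pain, and its agreement with the primary result would carry no information on that question. The cancellation is exact with complete data. It is close to exact when visits are missing at random independently of the covariate, and it does not depend on the assumed effect sizes. The 0.06 SD (16% of 0.37 SD) is illustrative and rests on the assumed imbalance and effect on change.

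A reader might infer that the primary result is biased or its test invalid. The documents do not support that: allocation is randomised and stratified, chance imbalance does not invalidate the test, and an imbalance in pain level alone is already removed by the change contrast. The Poisson models for health care use are unaffected, and the depression subgroup model already has its time interactions. This is a defect in one prespecified secondary analysis, worth correcting because the repair is nearly free.

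**What to change.** In the SAP's imbalance rule, and in Protocol 9.4.2 to match, enter each selected baseline variable with its interaction with visit. Keep the reported contrast as time × arm at 6 months (12 months for COMM, which has no 6-month measurement). State whether the baseline score is part of the response. If the sponsor instead intends to model post-baseline scores with baseline pain as a covariate, main effects suffice and the SAP should describe that model.

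Baseline depression × visit (3 parameters) may be added to the mixed models for a small precision gain. Site × visit is optional, for the reasons given above.

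Cost: one sentence, no new data, and 3 parameters per continuous or two-level variable with four visits. In the complete-data simulation, all the visit interactions together (18 + 3 + 3 = 24 parameters) raised the mean standard error from 0.1080 to 0.1093, about 1%.
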